9.4 Study Drug Dosage and Dose Regimen

All infusions of AK002 will be 3 mg/kg. Dosing will occur on Extension Days 1, 29, 57, 85, 113, 141, 169, 197, 225, 253, 281, 309, 337, 365, 393, 421, 449, and 477 (± 3 days).

The exact amount of AK002 to be mixed with NaCl will be calculated prior to each infusion and based on current patient body weight. Study drug will be administered as a single peripheral intravenous infusion using an infusion pump as indicated in the study Pharmacy Manual at the study visits specified in [Table 1](#).

9.5 Preparation of Study Drug

A study pharmacist or designee will prepare the study drug for each infusion. Based on patient body weight obtained the day of or the day prior to dosing, the designated study pharmacist will prepare the appropriate dilution of AK002 for intravenous administration.

Appropriate aseptic technique will be used, and the drug will be prepared according to the pharmacy manual for AK002. Refer to the Pharmacy Manual for additional details and step-by-step instructions regarding study drug preparation.

The infusion must be completed within 8 hours of preparation. Preparation is when AK002 is first mixed with NaCl.

9.6 Study Drug Administration

Specific instructions on administration and supplies required for administration are detailed in the Pharmacy Manual. In general, study drug will be infused through a peripheral vein intravenous set. The intravenous line should be kept open before and after the infusion with sufficient quantities of 0.9% NaCl to assure patency.

A volume of 100 mL* of the calculated dose of study drug will be infused over at least 4 hours on Extension Day 1, over at least 2 hours on Extension Days 29 (± 3), 57 (± 3), 85 (± 3), 113 (± 3), and 141 (± 3) and over at least 1 hour from Extension Day 169 (± 3) and onwards. If the infusion is slowed or interrupted, the time may be extended longer than 4 hours, as long as it does not exceed 8 hours.

* Due to the rounding of the total infusion volume by some programmable infusion pumps, an infusion of 99 mL to 101 mL will be considered a complete infusion and will not be recorded as a deviation of the study.

Due to programming limitations of some infusion pumps, all volumes associated with the infusion may be rounded to the nearest 1/10th mL.

For the first infusion of study drug, patients will be premedicated with 80 mg oral prednisone (or approved equivalent) 12–24 hours prior to the start of the study drug infusion. For subsequent infusions, premedication may only be used at the discretion of the Investigator and with the written approval of the Medical Monitor.

The IV infusion may be interrupted and/or the rate may be reduced if a patient has an IRR. The time the infusion is initiated/concluded (including any interruptions) will be documented in the eCRF. If the infusion is restarted after an interruption, the infusion must be completed within 8 hours of preparation. Administration will be discontinued if, in the opinion of the Investigator,

an interrupted infusion cannot be restarted for safety reasons or if the infusion cannot be completed within 8 hours of preparation. Administration will also be discontinued in any patient experiencing a serious adverse event during the course of the infusion.

The patient will be observed at least 1 hour after the end of each infusion, as per Investigator discretion.

9.7 Study Drug Storage

AK002 will be stored by the study sites at 2°–8°C in a secured, restricted, and temperature-monitored location in the designated pharmacy, pending drug preparation. The 0.9% NaCl will be stored at ambient temperature, per manufacturer's requirements. Study drug will be stored in an area that is temperature controlled and monitored. If the temperature of study drug storage in the clinic/pharmacy exceeds or falls below this range, it will be reported to the Sponsor using the guidelines in the Pharmacy Manual. The Sponsor will notify the site if the study drug is to be quarantined or can be used.

9.8 Temperature Excursions

AK002 is stable at 2°–8°C. In case of temperature excursion during shipping, or if the temperature of drug storage in the pharmacy exceeds or falls below 2°–8°C, please contact Allakos immediately by sending the completed Site Temperature Excursion Form to [contact] (email) or [name] (fax) before any use of the investigational product (IP). Attach all available information with the Site Temperature Excursion Form including temperature logs showing the extent and duration of the excursion.

The IP exposed to the temperature excursion should be quarantined until Allakos determines whether the IP is compromised or approved for use. Allakos or designee will provide written instructions regarding use of the IP, and these instructions should be added to the pharmacy study file.

9.9 Study Drug Accountability

The site's study pharmacist/designee is responsible for maintaining accurate and current records accounting for the receipt, dispensing, preparation, use, return (or destruction), and final disposition of all investigational product. All dosage calculations will be documented on the source documents. The Master Investigational Product Accountability Log, or similar form, should be used to capture receipt, dispensing, and return (or destruction). Electronic IP accountability systems may be used depending on site preference, as long as the same information is captured. The study monitor will verify entries on these documents throughout the course of the study.

10. Patient Numbering, Stratification, Randomization, and Blinding

10.1 Patient Numbering

Each patient who provides informed consent will be identified by the PID assigned in Study AK002-016 or Study AK002-012. The patient will maintain the same PID throughout the study.

A patient is considered enrolled in the AK002-016X study when the subject receives the first dose of open-label AK002.

10.2 Stratification and Randomization

There will be no randomization or stratification as all patients will receive AK002.

10.3 Blinding

There will be no blinding as all patients will receive AK002.

11. Study Procedures and Guidelines

[Table 1](#) provides the schedule of assessments, depicting the required testing procedures to be performed for the duration of the study.

When multiple evaluations are scheduled at the same time point, the priority for each will be as follows:

- SF-36 (self-administered format) should be completed at the beginning of the study visit before any other assessments or procedures.
- PRO questionnaire should be completed by each study subject daily (at approximately the same time each day) during the treatment and follow-up periods.
- Vital signs will be obtained after the patient has been at rest for ≥ 5 minutes.
- Physical examinations (if needed) can be performed, and urine samples can be collected either before or after other evaluations.

11.1 Dietary and Lifestyle Restrictions

The extension study does not include fasting requirements. Patients underwent a standardized baseline evaluation of eating habits, food habits/restrictions, and food avoidance behaviors during Study AK002-016 and Study AK002-012 and will be asked to maintain the same diet through the first 6 months of the study. After the seventh dose has been received, diet and eating habits may be liberalized as desired, with all changes noted in the CRF.

11.2 Pharmacodynamic/Efficacy-Related Procedures

11.2.1 EG/EoD PRO Questionnaire

An electronic version of the PRO questionnaire ([Appendix 1](#)) will be completed daily at approximately the same time of day, by the patient, throughout the study.

Patients will not be able to complete a questionnaire more than 24 hours after it is due and will only be able to go back and make corrections or changes to the data originally entered with the approval of the Investigator and EDC vendor. The PRO information will be automatically captured and maintained in the ePRO system of the EDC.

A paper version of the PRO questionnaire is available to patients in case they are not able to complete the electronic version for a short period of time. Only 1 PRO should be completed per day, and the recall period should not be any more than approximately 24 hours long.

The information will be manually captured and entered into the EDC by the study site.

If patients have a history of concomitant atopic dermatitis or asthma, an extra question will be populated for each relevant condition on the PRO website for the patient to complete daily.

A paper version of these questions is available if the website is not accessible or the patient does not have Internet access ([Appendix 5](#)). Additionally, patients that received the dysphagia question in the AK002-016 study will continue to receive the question in the extension study.

11.2.2 Short Form-36 Health and Well-Being Survey

An electronic version of the SF-36 Health and Well-Being Survey ([Appendix 2](#)) will be completed by the patient on all dosing days (predose), as well as on extension Days (± 3) 512, 533, and 561 or 35, 56, and 84 (± 3) days after last dose of study drug if ET.

If the questionnaire was already completed within the last 28 days as part of the last study visit in the AK002-016 study, a duplicate entry is not required on extension Day 1.

A paper version of this questionnaire will also be available for completion in case the electronic questionnaire is not available to the patient. This information will be entered into the EDC by the study site.

11.2.3 Complete Blood Count with Differential

Blood will be obtained for CBC with differential predose and 1 hour (± 15 minutes) postdose on all infusion days, as well as on Days 512 (± 3), 533 (± 3), and 561 (± 3) or 35, 56, and 84 (± 3) days after last dose of study drug if ET. If already collected within the last 28 days as part of the last study visit in the AK002-016 study, a duplicate predose collection on extension Day 1 is not

required. For patients entering the study from AK002-016, all differential cell counts will remain blinded.

The blood sample will be processed and shipped in accordance with the central laboratory manual and laboratory kit instructions. A central laboratory will analyze the blood sample and provide results for CBC with differential, including hemoglobin, hematocrit, platelet count, red blood cell count, white blood cell count, and absolute differential count (neutrophils, lymphocytes, monocytes, eosinophils, and basophils).

11.2.4 Esophago-Gastro-Duodenoscopy with Biopsy

An EGD with biopsy will be performed on Day 211 (± 3) and Day 505 (± 3) or 28 (± 3) days after last dose of study drug if ET. Biopsy samples will be collected according to standardized instructions and will be sent to the central laboratory (or designee) for fixing and staining. A central reader will report, among other things, maximum number of eosinophils/hpf and maximum number of tryptase-positive mast cells/hpf, and gastric biopsies will be graded using the Sydney System on inflammation, metaplasia, atrophy, and reactive gastropathy. The Marsh Scale Classification will be used to grade duodenal samples. The baseline EGD from Study AK002-016 will be used for comparison.

11.2.5 Baseline Diet Assessment

During the AK002-012 and AK002-016 studies, the Investigator or designee asked patients a standardized series of dietary assessment questions. The baseline diet should be maintained as much as possible through the first 6 months of the extension study even if symptoms improve. After the seventh infusion has been received, patients may liberalize their diets and make changes from the baseline diet, as desired. Changes from the baseline diet will be assessed at every study visit and 35, 56, and 84 (± 3) days after last dose if ET.

11.3 Safety-Related Procedures

11.3.1 Concomitant Medications

All ongoing concomitant medications and therapies will be transferred from Study AK002-016 into Study AK002-016X. Any medications used for premedication during the conduct of the EGD or for treatment of IRR will be documented in the AK002-016X Concomitant Medications Log. Dose, route, unit, frequency of administration, indication for administration, and dates of medication will be captured. Any medication received during the study through Extension Day 561 (± 3) or 84 (± 3) days after last dose of study drug, if ET, will be recorded.

11.3.2 Body Weight

Body weight will be measured predose and used to determine the amount of study drug to be mixed with NaCl for each infusion. Body weight must be measured on the day of, or on the day prior to, the day of each infusion. Body weight will be entered into the interactive response technology (IRT) system for each dosing visit and will also be recorded on the Investigational Product Dose Calculation and Preparation Worksheet that the pharmacist or designee will maintain to document each patient's dose calculations.

Body weight should be collected on site on the day of each study drug infusion or on the day prior to each infusion. Body weight will also be captured on Days 512, 533, and 561 (± 3) or 35, 56, and 84 (± 3) days after last dose of study drug if ET.

11.3.3 Symptom-Directed Physical Examination

A symptom-directed physical examination, an examination of reported or observed patient symptoms warranting examination (in the opinion of the Investigator) including assessments of possible infusion site reactions and IRR, will be performed by either the Investigator or a qualified designee at all study visits through Extension Day 561 or 84 (± 3) days after last dose of study drug if ET. New, abnormal, and clinically significant physical examination findings must be documented and will be followed by the study doctor or Subinvestigator at the next scheduled visit or sooner if clinically indicated or referred to a non-study physician.

11.3.4 Vital Signs

Vital signs, including systolic and diastolic blood pressure, pulse, body temperature, and respiratory rate, will be taken after the patient has been at rest for ≥ 5 minutes and before any blood draw (except for post-infusion for which vital signs will be obtained as described below).

On dosing days, vital signs will be measured within 30 minutes predose, within 30 minutes after the start of infusion, and within 30 minutes following the end of infusion. Refer to the schedule of assessments in [Table 1](#).

Investigators may have additional vital sign procedures performed for the purpose of treatment administration or following AE.

11.4 Clinical Laboratory Measurements

Blood and urine samples for clinical safety laboratory tests will be collected at the time points presented in [Table 1](#). Investigators may have additional laboratory tests performed for the purpose of planning treatment administration or following AE or abnormal laboratory values.

The site will process and ship blood and urine samples per central laboratory instructions. A central laboratory or designee will analyze blood and urine samples and provide results for the clinical safety laboratory tests.

Clinical laboratory testing may be performed locally if the site thinks the central laboratory may not be able to provide results in a timely fashion due to staff reductions, shipping issues, or other factors associated with the COVID-19 pandemic. The site will strive to use the central laboratory whenever possible.

For any laboratory test value outside the reference range, the Investigator will determine clinical significance (Not Clinically Significant [NCS] or Clinically Significant [CS]). An abnormal lab value should be deemed CS if any of the following conditions are met:

- The abnormality suggests a disease and/or organ toxicity that is new or has worsened from baseline.
- The abnormality is of a degree that requires additional active management, e.g., change of study drug dose, discontinuation of the study drug, close observation, more frequent follow-up assessments, or further diagnostic investigation.

Therefore, a clinically significant lab value is one that indicates a new disease process, an exacerbation or worsening of an existing condition, or requires further action to be taken.

For any laboratory test value outside the reference range that the Investigator considers clinically significant, the Investigator will:

- Repeat the test to verify the out-of-range value.
- Follow the out-of-range value to a satisfactory clinical resolution.
- Record as an AE any laboratory test value after start of study drug that:
 - The Investigator considers clinically significant
 - Requires a patient to be discontinued from the study or
 - Requires a patient to receive treatment

11.4.1 Complete Blood Count with Differential

Blood will be obtained for CBC with differential as described in Section 11.2.3. If already collected within the last 28 days as part of the last study visit in AK002-016, a duplicate predose collection on Extension Day 1 is not required for AK002-016X. The postdose collection on Day 1 is still required.

11.4.2 Blood Chemistry Profile

Blood for chemistry tests will be processed and shipped in accordance with the central laboratory manual and laboratory kit instructions.

If already collected within the last 28 days as part of the last study visit in AK002-016, a duplicate predose collection is not required on Extension Day 1. Blood will be obtained predose on all dosing days as well as on Days 512, 533, and 561 or 35, 56, and 84 (± 3) days after last dose of study drug if ET.

A central laboratory will analyze the serum sample and provide results for chemistry tests including sodium, potassium, chloride, bicarbonate, glucose, blood urea nitrogen, creatinine, creatine kinase, calcium, phosphorus, magnesium, total and direct bilirubin, total protein, albumin, aspartate aminotransferase, alanine aminotransferase, alkaline phosphatase, gamma-glutamyl transferase, and lactate dehydrogenase.

11.4.3 Pregnancy Test

For patients of childbearing potential, the site will perform a urine dipstick pregnancy (hCG) test prior to each infusion, as well as on Day 512 (± 3) or 35 (± 3 days) after last dose of study drug if ET. The site will perform the urine pregnancy test using an indicator stick from the pregnancy test kit supplied by the central laboratory and using urine collected for the urinalysis. This test will be assessed prior to the start of each study drug infusion. If already tested within the last 28 days as part of the last study visit in AK002-016, a duplicate test is not required on Extension Day 1. If a patient has a positive pregnancy test, dosing will immediately be discontinued.

To ensure patient safety, each pregnancy in a patient that received study drug must be reported within 24 hours of learning of its occurrence. If the patient received AK002, the pregnancy should be followed to determine outcome, including spontaneous or voluntary termination, details of the birth, and the presence or absence of any birth defects, congenital abnormalities, or maternal and/or newborn complications.

Women who are surgically sterile (tubal ligation, hysterectomy, or bilateral oophorectomy) for at least 3 months or those who are postmenopausal for at least 1 year with FSH level >30 mIU/mL are not considered to be of childbearing potential.

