5.2 Schedule of Events

The overall schedule of procedures and assessments are depicted in [Table 1](#).

Table 1 Schedule of Assessments

		Extension Treatment Period (18 months)				Extension Follow-Up Period (12 weeks)				
		Dose 1	Doses 2-7	Dose 8	Day 211	Doses 9-18	EGD	Follow-up #1	Follow-up #2	Follow-up #3
Prior to First Dose	Assessments	Extension Day 1 85, 113, 141, 169 (± 3 days)	Day 29, 57, 85, 113, 141, 169 (± 3 days)	Day 197 (± 3 days)	(± 3 days)	Day 225, 253, 281, 309, 337, 365, 393, 421, 449, 477 (± 3 days)	Day 505 (± 3 days) or 28 days after last dose if ET	Day 512 (± 3 days) or 35 days after last dose if ET	Day 533 (± 3 days) or 56 days after last dose if ET	Day 561 (± 3 days) or 84 days after last dose if ET
Informed consent	X									
Medical History ¹	X									
Prior/Concomitant Medications ²	X ³	X	X	X	X	X	X	X	X	X
Baseline Diet Assessment/Compliance	X ³	X	X	X	X	X	X	X	X	X
Body weight ⁴	X(predose) ³	X(predose)	X(predose)	X(predose)	X(predose)	X(predose)	X	X	X	X
Vital signs ⁵	X	X	X	X	X	X	X	X	X	X
Symptom-directed Physical Exam ⁶	X ³	X	X	X	X	X	X	X	X	X
Eligibility assessment	X	X								
ePRO Training and Activation ⁷	X									
ePRO Questionnaire (may include additional questions) ⁸										
SF-36 Health Survey ⁹		X ³	X	X	X	X	X	X	X	X
Dysphagia Question										
Dipstick Pregnancy Test ¹⁰	X ³ (predose)	X(predose)	X(predose)	X(predose)	X(predose)	X(predose)	X			
Access IRT to enter Patient ID and current body weight ¹¹	X(predose)	X(predose)	X(predose)	X(predose)	X(predose)	X(predose)				
Premedication: prednisone ¹²	X ²¹									
Study drug administration ¹³	X ²²	X	X	X	X	X	X	X	X	X

<-----Perform daily from Day 1 through Day 561 or 84 days after last dose, if ET----->
 <-----Perform daily from Day 1 through Day 561 or 84 days after last dose, if ET----->

Table 1 Schedule of Assessments cont.

Assessments	Prior to First Dose	Extension Treatment Period (18 months)				Extension Follow-Up Period (12 weeks)			
		Dose 1	Doses 2-7	Dose 8	Day 211	Doses 9-18	EGD Follow-up	Follow-up #1	Follow-up #2
Blood for CBC with differential ^{14,15}	X	X	X	X	X	X	X	X	X
Blood for chemistry ^{14,16}	X (predose) ³	X (predose)	X (predose)	X (predose)	X (predose)	X (predose)	X	X	X
Urinalysis ^{14,17}	X (predose) ³	X (predose)	X (predose)	X (predose)	X (predose)	X (predose)	X	X	X
Blood for pharmacokinetics ^{14,18}	X (predose) ³	X (predose)	X (predose)	X (predose)	X (predose)	X (predose)	X	X	X

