Blood for ADA ^{14,19}	X (predose) ³	X (predose)	X (predose)	X (predose)	X (predose)	X (predose)	X	X	X
Blood for Total Serum IgE ^{14,20}	X (predose) ³						X	X	X
EGD with biopsy ²³					X		X	X	X
Non-serious adverse events ²⁴	X	X	X	X	X	X	X	X	X
Adverse events of special interest ²⁵	X	X	X	X	X	X	X	X	X
Serious adverse events ²⁶	X	X	X	X	X	X	X	X	X

CBC: Complete Blood Count

EGD: Esophago-Gastro-Duodenoscopy

ET: Early Termination

IRT: Interactive Response Technology

Table Notes

- 1) Record all pertinent, ongoing medical history as well as any significant adverse events (AE) that occurred in the AK002-016 or AK002-012 study but resolved before the first dose in the extension study.
- 2) Record all concomitant medications taken within 30 days of Extension Day 1 and during the course of the study. Record all concomitant medication received during EGD, any premedication given, and any medication used for the treatment of IRR.
- 3) Do not collect if procedure was performed as part of the last study visit in AK002-016 (on Day 176, 197 or 225, depending on when patient receives first dose in AK002-016X). Differential cell counts collected for Study AK002-016X postdose CBC with differential is still required 1 hour (± 15 minutes) after the first AK002-016X infusion ends.

Table Notes cont.

- 4) Body weight will be measured predose and recorded in kilograms (kg) on Day 1, all infusion days, and at Follow-up visits on Days 512, 533, and 561 or 35 (± 3), 56 (± 3), and 84 (± 3) days after last dose of study drug if ET. Body weight is to be measured in kg as it is used to determine patient dosing calculations
- 5) Vital signs including systolic and diastolic blood pressure, pulse, body temperature, and respiratory rate will be taken after the patient has been at rest for ≥ 5 minutes and before any blood draw. Vital signs will be measured on all dosing days within 30 minutes predose, within 30 minutes after the start of infusion, and within 30 minutes following the end of infusion.
- 6) A symptom-directed physical examination (including assessment of possible infusion site reactions) will be performed by the Investigator or designee, as needed if any significant symptoms or changes from baseline are reported.
- 7) Activate PRO questionnaire and provide patient with unique username and password. Use ePRO Teaching Tool for patient training and reference. PRO questionnaire should be activated for all patients on Day 1.

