7.4 Exclusion Criteria

Patients will be excluded from the study if they meet any of the following criteria:

- 1) Poor tolerance to previous administration of AK002 in the opinion of the Investigator.
- 2) Known hypersensitivity to any constituent of the study drug.
- 3) Any disease, condition (medical or surgical), or cardiac abnormality, which, in the opinion of the Investigator, would place the patient at increased risk.
- 4) Planned or expected vaccination with live attenuated vaccines during the treatment period, or vaccination expected within 5 half-lives (4 months) of AK002 administration. All types and formulations of vaccines (including live attenuated vaccines) authorized by FDA or other regulatory authority for the prevention of COVID-19 may be administered before, during, or after this study. The vaccine should not be administered within 7 days prior to and within 7 days after the administration of AK002 so that any side effects caused by either of the 2 medications can be more easily determined.
- 5) Women who are pregnant, breastfeeding, or planning to become pregnant while participating in the study.
- 6) Any other reason that, in the opinion of the Investigator or Medical Monitor, makes the patient unsuitable for enrollment.

8. Concurrent Medications

Prior and concomitant medications include both prescribed and over-the-counter medications and will be recorded in the electronic Case Report Forms (eCRF). Medications taken for EG/EoD or symptoms of EG/EoD, as well as any medications taken within 30 days prior to extension study Day 1 should be recorded.

Medications taken prior to the study should be maintained, as much as possible. Patients should be advised against taking any new medication or stopping an existing medication, both prescribed and over-the-counter, without consulting the Investigator, unless the change is required for emergency use. Immediately prior to the first infusion, the study site personnel should ensure that the patient continues to meet the inclusion criteria and none of the exclusion criteria (including use of prohibited medications as per AK002-016 criteria).

All medications used during the conduct of the study must be documented.

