11.4.5 Urinalysis

Urine samples will be processed and shipped in accordance with the central laboratory manual and laboratory kit instructions. Urine will be obtained on Extension Days 1, 197, and 512 or 35 (± 3) days after last dose of study drug if ET. If already collected within the last 28 days as part of the last study visit for AK002-016, a duplicate collection is not required on Extension Day 1. A central laboratory will analyze the urine sample for specific gravity, pH, protein, glucose, ketones, blood, and leukocyte esterase.

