12.2 Extension Day 1 – First Day of Dosing

The following procedures will be performed prior to study drug infusion:

- Confirm continuing eligibility for the study.
- Activate patient access to ViedocME website and instruct patient on use of the website to complete the questionnaire(s). Use the ePRO Teaching Tool (Appendix 4) to remind patients on the use of the electronic platform.
- Have patient complete SF-36 Health Survey. Obtain from last study visit of AK002-016 if the visit occurred within 28 days prior to Extension Day 1.
- Determine body weight (in kg).
- Enter PID and body weight (in kg) into IRT.
- Document any changes in baseline diet. Obtain from last study visit of AK002-016 if the visit occurred within 28 days prior to Extension Day 1.

- Collect vital signs within 30 minutes of the start of the infusion.
- Perform symptom-directed physical examination, as needed. Obtain from last study visit of AK002-016 if the visit occurred within 28 days prior to Extension Day 1.
- Collect blood samples for CBC, blood chemistry, IgE, ADA, and PK. Obtain from last study visit of AK002-016 if the visit occurred within 28 days prior to Extension Day 1. Differential cell counts from AK002-016 will remain blinded.
- Collect urine for urinalysis. Obtain from last study visit of AK002-016 if the visit occurred within 28 days prior to Extension Day 1.
- Perform urine pregnancy test. Obtain from last study visit of AK002-016 if the visit occurred within 28 days prior to Extension Day 1.
- The study pharmacist will prepare study drug at **3 mg/kg** using the body weight obtained at the visit or the day prior to Extension Day 1. The final combined volume of the IV bag of study drug + 0.9% NaCl will be **120 mL**.

Note: **100 mL** of the calculated volume of study drug/NaCl mixture will be administered to the patient. The extra 20 mL is to be used to prime the IV infusion line during the preparation of the IV line or to be left over in the infusion bag/tubing when the infusion is completed.

Procedures associated with the infusion of study drug include:

- Infuse 100 mL of study drug over at least 4 hours using an infusion pump. Refer to the Pharmacy Manual for infusion rates. Record the start and stop times of the infusion including any times the infusion is interrupted.
- Collect vital signs within 30 minutes after the start of infusion.

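### The pregnancy test may be carried over at Dose 1, the only one of 18 infusions that can be given without a same-visit test

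*Combined protocol and SAP*

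**What the plan says.** Section 11.4.3 sets the general rule: patients of childbearing potential have a urine hCG dipstick before each infusion, read before the infusion starts, and a positive result stops dosing at once. Table 1 note 10 says the same for all infusion days. The visit lists for Doses 2 to 18 (Sections 12.3 to 12.11) each include the test and give no exception.

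For AK002-016 entrants, Extension Day 1 is treated differently in three places:

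- Section 11.4.3: "If already tested within the last 28 days as part of the last study visit in AK002-016, a duplicate test is not required".
- Section 12.2: "Perform urine pregnancy test. Obtain from last study visit of AK002-016 if the visit occurred within 28 days prior to Extension Day 1".
- Table 1: the Extension Day 1 cell of the "Dipstick Pregnancy Test" row carries superscript 3, and note 3 reads "Do not collect if procedure was performed as part of the last study visit in AK002-016".

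The sample is waived too. The dipstick is done "using urine collected for the urinalysis" (Section 11.4.3). For the Extension Day 1 urine, Section 11.4.5 says "If already collected within the last 28 days as part of the last study visit for AK002-016, a duplicate collection is not required"; Section 12.2 says "Collect urine for urinalysis. Obtain from last study visit of AK002-016 if the visit occurred within 28 days prior to Extension Day 1".

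Section 8 adds an eligibility check: "Immediately prior to the first infusion, the study site personnel should ensure that the patient continues to meet the inclusion criteria". Section 12.2 also asks for eligibility to be confirmed. Neither asks for a new pregnancy test.

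**The concern.** The waiver handles the pregnancy test in the same way as chemistry and urinalysis. It differs from them in two respects: the answer can change within the permitted interval, and it decides whether the patient may be dosed.

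Under Section 10.1 a patient is enrolled when she receives the first dose. That is the moment when inclusion criterion 5 (negative test) and exclusion criterion 5 (not pregnant) in Sections 7.3 and 7.4 must hold. For a patient who had placebo in AK002-016, it is also the first AK002 infusion. A site that follows the text exactly can give that infusion on a negative result that is no longer current, and a positive test at Extension Day 29 comes after the exposure.

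The plan's own standard is stricter everywhere else. Doses 2 to 18 are 28 days apart and each needs a fresh test, so a negative from the previous dosing visit never suffices there. At Dose 1, a result up to 28 days old does.

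**Working it through.** This is schedule arithmetic on nominal visit days.

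**Inputs.** Dosing on Extension Days 1, 29, … 477 (Section 9.4). Entry from 1 day after the Day 176 visit. The Day 197 and Day 225 main-study visits take place if the patient has not enrolled before them, and entry closes at Day 225 (Section 5.1). The carry-over limit is 28 days in Sections 11.4.3 and 12.2, 28 (± 3) days in the general rule of Section 5.1, and unstated in Table 1 note 3.

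**The plan's own count.** Days 1 + 28i for i = 0 to 17 give exactly the 18 listed dosing days, ending at 1 + 28 × 17 = 477. Doses 2 to 18 have an unconditional same-visit test, which is 17 of 18. Only Dose 1 can rely on a carried-over result.

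**Age of the result.** Age = main-study day of Dose 1 minus day of the last test. Extension Day 29 is 28 days after Extension Day 1, so the gap between consecutive tests is age + 28.

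| Path | Test day | Dose 1 day | Age (days) | Gap to next test (days) |
|---|---|---|---|---|
| Ordinary | 176 | 177 | 1 | 29 |
| Delayed, just before the Day 197 visit | 176 | 196 | 20 | 48 |
| Same, Day 176 visit held 3 days early | 173 | 196 | 23 | 51 |
| Conditional: AK002-016 also tests at Day 197 | 197 | 224 | 27 | 55 |

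For comparison, tests at consecutive later doses are 28 days apart, and the last interval is 512 − 477 = 35 days.

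**How likely is the conditional row?** The documents do not show which AK002-016 visits include a pregnancy test. If its six infusions were 28 days apart (an assumption), the last fell on Day 1 + 28 × 5 = 141, and Days 176, 197 and 225 are 35, 56 and 84 days later. Those are the extension's own follow-up offsets, and in the extension only the 35-day visit has a pregnancy test (Section 12.13, against 12.14 and 12.15). If AK002-016 follows the same pattern, a patient whose last visit was Day 197 has no result to carry over and must be tested on Extension Day 1. The 27-day case is therefore unlikely, and the realistic exposure is starts on Days 177 to 196.

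**Scale of the risk.** Section 11.4.4 lists methods at 91% to 99% effective. Treating these as annual, single-method rates (an assumption), the chance of conception over 20 days is between 0.01 × 20/365 = 0.05% and 0.09 × 20/365 = 0.5% per woman. Over 1 day it is between 0.01/365 = 0.003% and 0.09/365 = 0.02%. The dual contraception or abstinence required by Section 7.3 should lower these figures.

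**The case against.** The waiver is deliberate. It appears in three places and follows from the general rule against duplicate procedures in Section 5.1 and the synopsis. On the ordinary path the result is about 1 day old, so the point reaches only delayed starters, whose number is not given. It applies only where AK002-016 did a test at the last visit, and it does not cover AK002-012 entrants. Section 11.4.3 permits a repeat test, and Section 11.4 lets investigators order extra tests when planning treatment, so a site with any doubt may test. Note 3's missing age limit has little practical force, because the visits it names are at most 28 days apart. The per-woman risk is a fraction of a percent. Patients already on AK002 may still have drug on board (Section 7.4 equates five half-lives with 4 months), so a Day 1 test prevents less new exposure for them. Finally, text edits mean a protocol amendment with IRB approval and investigator signatures (Section 17.1) at approximately 60 centers.

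All of this stands as a matter of weight. It does not remove the point. Permission to test is not a requirement, and a site working from note 3 is told not to collect. Contraception is required throughout the study, yet the plan still tests at every later dose. Exceptions to the carry-over rule already exist on Extension Day 1: the post-dose blood count remains required (Section 11.4.1), and vital signs are not carried over (Section 12.2).

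**Conclusion.** The point holds as a design choice worth revisiting. Dose 1 is the one infusion of 18 for which the plan does not require a same-visit pregnancy test, for AK002-016 entrants tested at their last main-study visit. The carried-over result is about 1 day old on the ordinary path and nominally up to 20 days old when it comes from Day 176. A 27-day-old result is possible only if AK002-016 also tests at Day 197, which the documents do not show and the extension's own schedule makes unlikely. The absolute risk is small and falls on delayed starters. It matters most for former placebo patients, for whom this is the first exposure. The day counts assume nominal visit days, apart from the one early-visit row. The risk figures also assume that the listed contraceptive rates are annual.

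**What to change.** Exempt the pregnancy test from the duplicate-procedure waiver:

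1. Section 11.4.3: delete the sentence containing the waiver.
2. Section 12.2: replace the pregnancy-test bullet with an instruction to collect urine from every woman of childbearing potential and test it at the visit, with no carry-over. This secures a sample even when the Day 1 urinalysis is waived.
3. Table 1: remove superscript 3 from the Extension Day 1 cell of the pregnancy-test row.
4. Section 5.1: except the urine pregnancy test from the 28 (± 3) day bullet.
5. Synopsis: make the same exception in the matching bullet.

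The urinalysis waiver can stay.

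The cost is one urine sample and one on-site dipstick per AK002-016 entrant of childbearing potential. The number of such women is not given; the enrolment ceiling in Section 7.1 bounds it at about 183. Kits are already supplied for the other 17 infusions and patients already attend the visit. The edits need an amendment, so the sensible course is to include them in the next one. A Day 1 dipstick will still miss very recent conceptions.
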